9.5 Safety and Tolerability Assessments

9.5.1 Adverse events

Where changes in severity are recorded in the Case Report Form (CRF), each separate severity of the AE will be reported in the listings, only the most severe will be used in the summary tables. A pre-existing condition is defined as an AE that starts before the subject has provided written informed consent and is ongoing at consent. A non-treatment emergent AE is defined as an AE which starts after informed consent but prior to dosing. A treatment-emergent AE is defined as an AE which occurs postdose or which is present prior to dosing and becomes more severe postdose.

All AEs will be listed. Treatment-emergent AEs will be summarized by treatment, severity and relationship to the study drug. The frequency (the number of AEs, the number of subjects experiencing an AE and the percentage of subjects experiencing an AE) of treatment-emergent AEs will be summarized by treatment, Medical Dictionary for Regulatory Activities (MedDRA) version 22.0 system organ class and preferred term. The summary and frequency AE tables will be presented for all causalities and those considered related to the study drug by the investigator. Any serious AEs will be listed.

Discontinuations due to AEs will be listed.

9.5.2 Glucose Monitoring and Hypoglycemia

During the study, blood glucose concentrations will be monitored for safety assessments. Glucose data will be listed, and if sufficient data is collected, summarized by treatment together with changes from baseline, where baseline is defined as Day 1 predose.

Hypoglycemic events will be appropriately recorded in the CRF. In the case of a hypoglycemic event, the actual blood glucose value, if measured, will be recorded in the CRF, together with any treatments administered. Each category of hypoglycemic events (defined below) will be listed and summarized by treatment. Hypoglycemia is defined as follows:

Documented Glucose Alert Level (Level 1), Plasma Glucose (PG) ≤70 mg/dL (3.9 mmol/L):

- Symptomatic hypoglycemia: an event during which typical symptoms of hypoglycemia are accompanied by PG \leq 70 mg/dL (3.9 mmol/L)

- Asymptomatic hypoglycemia: an event not accompanied by typical symptoms of hypoglycemia but with PG \leq 70 mg/dL (3.9 mmol/L)

– Unspecified hypoglycemia: an event during which $PG \leq 70 \text{ mg/dL} (3.9 \text{ mmol/L})$ but no information relative to symptoms of hypoglycaemia

Documented Clinically Significant Hypoglycemia (Level 2) PG <54 mg/dL (3.0 mmol/L):

- Symptomatic hypoglycemia: an event during which typical symptoms of hypoglycemia are accompanied by PG <54 mg/dL (3.0 mmol/L)

- Asymptomatic hypoglycemia: an event not accompanied by typical symptoms of hypoglycemia but with PG <54 mg/dL (3.0 mmol/L)

- Unspecified hypoglycemia: an event during which PG $\leq 4 \text{ mg/dL} (3.0 \text{ mmol/L})$ but no information relative to symptoms of hypoglycemia was recorded.

Severe hypoglycemia (Level 3): an event requiring the assistance of another person to actively administer carbohydrate, glucagon, or other resuscitative actions. During these episodes, the subject has an altered mental status and cannot assist in their care, is semiconscious or unconscious, or experienced coma with or without seizures and may require parenteral therapy. Plasma glucose measurements may not be available during such an event, but neurological recovery attributable to the restoration of blood glucose concentration to normal is considered sufficient evidence that the event was induced by a low PG concentration (\leq 70 mg/dL [3.9 mmol/L]).

Other Hypoglycemia:

Nocturnal hypoglycemia: any hypoglycemic event (documented symptomatic, asymptomatic, probable symptomatic, or severe hypoglycemia) that occurs between bedtime and waking

Investigator review of glucose results clinically indicative of hypoglycemia will be required.

9.5.3 Concomitant medication

Concomitant medication will be coded using the WHO drug dictionary (Version March 2019). Concomitant medication will be listed.

9.5.4 Clinical laboratory parameters

All clinical chemistry and hematology data will be summarized by parameter and treatment group together with changes from baseline, where baseline is defined as the Day 1 predose assessment, and listed. Urinalysis data will be listed. Additionally, clinical chemistry, hematology and urinalysis data outside the reference ranges will be listed and flagged on individual subject data listings.

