#### 10.3.1.2. Statistical Evaluation of Safety

Safety parameters that will be assessed include laboratory tests, vital signs, body weight, immunogenicity, hypoglycemic events, injection site reactions and ECG parameters. The parameters will be listed and summarized using standard descriptive statistics. Additional analyses may be performed if warranted based upon review of the data.

Laboratory measurements will be summarized regarding observed values and change from baseline by treatment group, at each time point, using descriptive statistics. In addition, all clinical chemistry, hematology, and urinallysis data outside the reference ranges will be tabulated by parameter and treatment group.

Vital signs will be summarized regarding observed values and change from baseline values by treatment at each time point using descriptive statistics. For change from baseline values, a mixed-model repeated-measure model with treatment, time (of measurement), and treatment-by-time interaction as fixed effects, participant as random effect, and baseline as covariate will be used to determine the effects of LY3493269. Least squares means as well as 90% confidence intervals (CIs) will be reported.

Electrocardiogram parameters will be summarized, including the PR, QT, RR, and QTcF intervals, QRS duration, and heart rate. Outliers for these parameters may be summarized by dose groups. A concentration response analysis will also be performed to assess the effect of LY3493269 on QTcF. Additional analyses may be performed to determine the effects of PK exposures on QTcF and other intervals.

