9. STATISTICAL METHODOLOGY

9.1 General

Data listings will be provided for all data that is databased. Summary statistics and statistical analysis will only be presented for data where detailed in this SAP. For continuous data, summary statistics will include the arithmetic mean, arithmetic standard deviation (SD), median, min, max and N; for log-normal data (e.g. the PK parameters: area under the concentration versus time curve [AUCs] and maximum observed drug concentration [C_{max}]) the geometric mean and geometric coefficient of variation (CV%) will also be presented. For categorical data, frequency count and percentages will be presented. Data listings will be provided for all subjects up to the point of withdrawal, with any subjects excluded from the relevant population highlighted. Summary statistics and statistical analyses will generally only be performed for subjects included in the relevant analysis population. For the calculation of summary statistics and statistical analysis, unrounded data will be used.

Mean change from baseline is the mean of all individual subjects' change from baseline values. Each individual change from baseline will be calculated by subtracting the individual subject's baseline value from the value at the timepoint. The individual subject's change from baseline values will be used to calculate the mean change from baseline using a SAS procedure such as Proc Univariate.

Data analysis will be performed using SAS[®] Version 9.4 or greater.

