9.5.13 Pancreatic Safety

Serum amylase and lipase measurements will be collected as part of the clinical laboratory testing at time points specified in the protocol Additional measurements may be performed at the investigator's discretion.

Further diagnostic assessments will be recommended whenever lipase and/or amylase are confirmed to be $\ge 3 \times$ ULN at any visit post-treatment sequence allocation even if the participant is asymptomatic. If pancreatitis is suspected, the case will be further defined during an adjudication process.

These data will be listed.

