11. CHANGES FROM THE PROTOCOL SPECIFIED STATISTICAL ANALYSES

There were no changes from the protocol specified statistical analyses.

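### SAP 9.5.4 replaces the protocol's by-treatment tabulation of out-of-range laboratory values with flagged listings and leaves urinalysis unsummarized, while SAP 11 declares no changes

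*SAP*

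**What the plan says.** Protocol 10.3.1.2 makes two commitments on laboratory data. The first is general: "Laboratory measurements will be summarized regarding observed values and change from baseline by treatment group, at each time point, using descriptive statistics". The second comes on top of it: "all clinical chemistry, hematology, and urinallysis data outside the reference ranges will be tabulated by parameter and treatment group".

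SAP 9.5.4 handles the same data in three parts:

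- Chemistry and hematology: "All clinical chemistry and hematology data will be summarized by parameter and treatment group together with changes from baseline", with Day 1 predose as baseline.
- Urinalysis: "Urinalysis data will be listed".
- Out-of-range values in all three: "clinical chemistry, hematology and urinalysis data outside the reference ranges will be listed and flagged on individual subject data listings".

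Three other SAP statements govern how the difference is read. SAP 9.1 says: "Summary statistics and statistical analysis will only be presented for data where detailed in this SAP". SAP 3 places the SAP above the protocol's statistical section and undertakes to point out substantial differences. SAP 11 says: "There were no changes from the protocol specified statistical analyses".

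**The concern.** A flag on a subject listing is not a tabulation by parameter and treatment group. The listing shows that a given participant had a high value on a given day. The tabulation shows how the abnormal values are spread over the dose groups. The protocol promised the second and the SAP provides the first.

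Safety and tolerability is the primary objective, and Protocol 10.3.1.2 puts laboratory tests among the safety parameters to be assessed. Each active group is planned at 6 participants, so the natural way to look for a dose pattern in an analyte is to ask how many of the six went out of range. On the SAP's text, that count would have to be compiled from listings. SAP 9.5.6 does provide such counts by treatment for QTcF (above 450, 480 and 500 ms, and increases above 30 and 60 ms), so the SAP accepts the principle for one safety measure and omits it for laboratory values, where the protocol asked for it.

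The declaration in SAP 11 matters separately. A reader of the study report who relies on it would believe that the protocol's laboratory analysis had been carried out as specified.

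**Working it through.** The plan gives no figure to reproduce. The check compares texts, with a short calculation on what the remaining summaries can show.

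1. **Out-of-range values.** Protocol 10.3.1.2 has them tabulated by parameter and treatment group, for chemistry, hematology and urinalysis. SAP 9.5.4 has them listed and flagged by subject, for the same three. The tabulation is gone.

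2. **Urinalysis.** The protocol's general commitment to summaries by treatment and time point makes no exception for urinalysis. SAP 9.5.4 summarizes chemistry and hematology and only lists urinalysis. Urinalysis therefore loses both the summary and the tabulation.

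3. **Does another SAP section restore the table?** No. SAP 9.5.12 lists the hepatic laboratory data and flags out-of-range values. SAP 9.5.13, on pancreatic enzymes, ends with "These data will be listed". SAP 9.5.14 lists, without summary, any safety assessment not covered elsewhere. SAP 9.1 then excludes any summary the SAP does not detail.

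4. **Which document governs?** Under SAP 3 the SAP does. The protocol's sentence therefore does not survive as a fallback, and the statement in SAP 11 is inaccurate on both points.

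5. **What is still shown by treatment?** SAP 9.1 gives N, mean, SD, median, minimum and maximum for continuous data. Protocol Appendix 2 places lipase, amylase, ALT, AST, ALP and total bilirubin in the chemistry panel, so SAP 9.5.4 summarizes them by treatment. Protocol Appendix 1 counts an abnormal laboratory finding as a possible adverse event, and SAP 9.5.1 gives numbers and percentages of participants with treatment-emergent events by treatment.

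6. **What do those summaries leave open?** Assume a group of 6, a complete dataset and one upper limit for all six.
   - At one visit, suppose the maximum is above the limit and the median below it. The median is the mean of the 3rd and 4th ordered values. With 4 or more high values, both of these would be high, and so would the median. The number high is therefore between 1 and 3, that is 1/6 = 17% to 3/6 = 50%.
   - Across visits, the schedule has 6 postdose laboratory visits (Days 2, 4, 8, 15, 29 and 43), plus an early-termination visit for those who leave early. If exactly one value is high at each of the 6 visits, this could be one participant six times (1/6 = 17%) or six participants once each (6/6 = 100%).

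   The maximum shows that an outlier exists. It does not show how many participants were affected.

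7. **Reach.** SAP 6 defines 8 treatment groups. The point concerns the parameters measured after dosing. Triglyceride, total cholesterol and HbA1c are screening-only in Appendix 2 and do not enter.

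**The case against.** The strongest reply is that little is lost. The named primary endpoints are treatment-emergent and serious adverse events, and both are reported. Every out-of-range value appears, flagged, in a listing, so counts can be derived at reporting. The study is not powered for hypothesis tests, and escalation rests on ongoing review of safety data rather than on an end-of-study table. All of this stands. It makes the point one of reporting and disclosure, not of lost information or participant protection.

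A second reply is that the TFL shells, which SAP 3 says describe the planned tables in detail, may contain the table. They may. That the table would not be produced is an inference from SAP 9.1 and 9.5.4. If the shells do contain it, the SAP text should say so.

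A third is that the protocol says only that the data will be tabulated. It does not promise numbers and percentages of participants, a split by baseline status, or rows at multiples of the upper limit. That is correct. A table of the abnormal values arranged by parameter and treatment could satisfy the protocol's words. A participant count is the most useful form of that table, but its exact layout is a choice.

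A fourth is that SAP 3 requires only substantial differences to be identified, and the sponsor may consider this one minor. That might excuse silence in SAP 9.5.4. It does not make an unqualified statement of no changes true.

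**Conclusion.** The inconsistency is real and should be corrected. As the SAP is written, there is no by-treatment count of out-of-range laboratory values as such and no by-treatment summary of urinalysis results, and SAP 11 is wrong to say that nothing changed. This rests on the SAP's text alone, without the TFL shells.

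Three stronger readings are tempting, and the documents do not support them.

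- A reader might infer that individual outliers would be hidden in group means. They would not, because the chemistry and hematology summaries include the minimum, median and maximum.
- A reader might infer from SAP 9.5.12 and 9.5.13 that liver and pancreatic tests are only listed. The routine tests are part of the chemistry panel and are summarized under SAP 9.5.4. Those two sections add listings and do not remove that summary.
- A reader might infer that the primary objective has no by-dose count of laboratory abnormalities at all. Those recorded as adverse events are counted by treatment.

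What remains is a moderate gap: the number of participants per dose who went out of range is not reported, urinalysis is unsummarized, and the change is undeclared.

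**What to change.** In SAP 9.5.4, restore the protocol's table: the number of participants with at least one postdose value below, and at least one above, the reference range, by parameter and treatment group, for chemistry, hematology and urinalysis. For urinalysis results without a numeric range, count abnormal results. Either add the by-treatment urinalysis summary that the protocol's general sentence covers, or declare its omission. Correct SAP 11 accordingly. If the sponsor prefers listings only, SAP 11 should say that the tabulation and the urinalysis summary were dropped, and why.

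Optional, and beyond what the protocol promised: split the counts by in-range or out-of-range status at Day 1 predose, and add rows at the monitoring thresholds already in Protocol 9.4.5.4 and 9.4.5.5 (lipase or amylase at least 3 times the upper limit of normal, ALT at least 3 times, ALP at least 2 times, total bilirubin at least 2 times).

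The cost is one table shell and a short amendment to SAP 11, using data already collected. The design, the assessments and the sample size are unaffected.

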9.5.5 Vital signs

Vital signs data will be summarized by treatment group together with changes from baseline, where baseline is defined as the Day 1 predose assessment. Figures of mean vital signs and mean changes from baseline profiles will be presented by treatment.

Values for individual subjects will be listed.

For change from baseline values, a mixed-model repeated-measure model with treatment, time (of measurement), and treatment-by-time interaction as fixed effects, subject as a random effect, and baseline as covariate will be used to determine the effects of LY3493269. Least-squares means as well as 90% CIs for the difference of LY3493269 compared with placebo will be

reported. An unstructured covariance structure will be used and a compound symmetry structure may be used if this fails to converge.

Example of SAS code (for the change from baseline analysis) as follows.

```
proc mixed data=xxx;
class treatment timepoint subject;
model change = baseline treatment timepoint treatment*timepoint
/residual ddfm=kr;
repeated timepoint / subject=subject type=UN;
lsmeans treatment*timepoint / cl pdiff alpha=0.1;
ods output lsmeans=lsm diffs=estims;
run;
```

The relationship between the time-matched LY3493269 concentrations and changes from baseline and mean time-matched placebo for all vital signs parameters will be explored graphically using a scatter plot. A regression analysis using a linear mixed-effects model will be performed. A plasma LY3493269 concentration- vital signs data analysis will be performed to assess the changes from baseline (Day 1 predose) and mean time-matched placebo for each vital sign relative to plasma LY3493269 concentrations across all active treatments. The change from baseline adjustment will be based on each individual subject's Day 1 predose value, and an additional placebo adjustment will be based on mean time-matched placebo values. The analysis will be performed by plotting double delta vital signs measurement against LY3493269 concentration as a covariate. The estimated regression line and associated 90% CI will be fitted on the plot and the p-value for the slope reported. Estimated delta vital signs result and 90% CI at the geometric mean C_{max} will also be presented.

Example of SAS code as follows:

```
proc mixed data=xxx;
  class subject;
  model DDchg = concentration / solution cl alpha=0.1 ddfm=kr;
  random subject;
  ods output estimates=est;
  ods output solutionf=sol;
run;
```

9.5.6 Electrocardiogram (ECG)

The ECG data will be obtained directly from the 12-lead ECG traces. These data include the PR, QT, RR, QRS duration and heart rate. In addition, QT interval corrected using Fridericia's formula (QTcF) will be calculated as follows:

$$QTcF = \frac{QT}{\sqrt[3]{60/HR}}$$

The mean of triplicate data will be used for reporting. The ECG data will be summarized by treatment group together with changes from baseline, where baseline is defined as the mean of the triplicate Day 1 predose assessments (-30, -15 and 0 minute). Figures of mean ECG data and mean changes from baseline will be presented by treatment. The frequency of subjects with a maximum increase from baseline in QTcF interval will be summarized for each treatment according to the following categories: >30 ms and >60 ms. In addition, the frequency of subjects QTcF postdose values, according to the following categories: >450 ms, >480 ms and >500 ms, will be summarized by treatment.

The relationship between the time-matched LY3493269 concentrations and changes from baseline and mean time-matched placebo on QTcF will be explored graphically using a scatter plot. A regression analysis using a linear mixed-effects model will be performed. A plasma LY3493269 concentration-QTcF analysis will be performed to assess the changes from baseline (Day 1 predose) and mean time-matched placebo in the QTcF interval relative to plasma LY3493269 concentrations across all active treatments. The change from baseline adjustment will be based on each individual subject's Day 1 predose value, and an additional placebo adjustment will be based on mean time-matched placebo values. The analysis will be performed by plotting double delta QTcF against LY3493269 concentrations, including all post dosing timepoints. A linear mixed-effects model will be performed on the double delta QTcF values and will include LY3493269 concentration as a covariate. The estimated regression line and associated 90% CI will be fitted on the plot and the p-value for the slope reported. Estimated delta QTcF and 90% CI at the geometric mean C_{max} will also be presented. The analysis will also be produced for heart rate and PR.

Example of SAS code as follows:

```
proc mixed data=xxx;
  class subject;
  model DDchg = concentration / solution cl alpha=0.1 ddfm=kr;
  random subject;
  ods output estimates=est;
  ods output solutionf=sol;
run;
```

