- g Monkey CV LOEL was determined in a single-dose safety pharmacology study (130-738). Cardiovascular findings at 0.05 mg/kg were limited to increases in heart rate, blood pressure and QRS duration. The effects declined as the systemic exposure decreased, but still notable by the end of the monitor phase (88 96 hrs postdose). The mean exposure at 18 hours postdose (approximate Cmax) from Study 130-738.

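### The concentration-QTcF, heart rate, PR and vital-sign regressions treat the mean of about 12 placebo participants as error-free, so the 90% CI at Cmax is too narrow and the slope p-value too small; IV times with no matching placebo record have no rule

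*SAP*

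**What the plan says.** Protocol 10.3.1.2 commits to the analysis: "A concentration response analysis will also be performed to assess the effect of LY3493269 on QTcF". SAP 9.5.6 carries it out on a double delta. The participant's Day 1 predose value is subtracted first, and then "an additional placebo adjustment will be based on mean time-matched placebo values". The example code is "model DDchg = concentration / solution cl alpha=0.1 ddfm=kr", with subject as the only random effect. It has no time term, no treatment term and no placebo records. The section asks for the fitted line with a 90% CI, the slope p-value, and the estimate with 90% CI at geometric mean Cmax. It repeats all of this for heart rate and PR.

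The data are specified as "relative to plasma LY3493269 concentrations across all active treatments" and "including all post dosing timepoints". The IV cohort is therefore included, although SAP section 5 gives it no placebo group.

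SAP 9.5.5 uses the same construction for vital signs: "The analysis will be performed by plotting double delta vital signs measurement against LY3493269 concentration as a covariate". That section also has a separate MMRM in which placebo is a treatment level ("lsmeans treatment*timepoint / cl pdiff alpha=0.1"). The MMRM carries the placebo error properly and is not at issue.

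**The concern.** A mean of 12 people is an estimate. Subtracting it from every active participant at a given time gives them all the same error, but the regression treats participants as independent and the subtracted value as known. This has two effects:

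- The between-subject part of the placebo error shifts all active values together. It goes into the intercept, and nothing in the reported standard error reflects it.
- The time-specific part is common to all active participants at each time. It can line up with the concentration-time curve and so be read as a slope.

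SAP 9.5.6 has no MMRM, so for QTcF, ECG heart rate and PR this regression is the plan's only placebo-adjusted interval. Protocol Table GZHA.2, footnote g, reports nonclinical "increases in heart rate, blood pressure and QRS duration", so heart rate is a known signal. An interval that falls short of its nominal coverage can appear to exclude an effect, or suggest one, without support from the data.

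The IV gap is a separate and smaller matter. The plan calls for all active treatments, and for ECG all postdose times, but a time-matched placebo mean does not exist at some IV times.

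**Working it through.** **Counts.** SAP section 5 gives 6 x 6 = 36 SC active, 6 x 2 = 12 placebo and 6 IV participants. The total of 54 reproduces the planned number of completers in SAP section 7. Pooling the 12 is inferred from the single SC placebo treatment in SAP section 6.

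**Analytic check at the mean concentration.** For active participant *i* at time *t* with no drug effect, the double delta is (b_i + e_it) - (mean placebo b + mean placebo e_t). If between-subject variance s² dominates, the model counts s²/n for n active participants, while the true variance is s²(1/n + 1/12). The true SE exceeds the reported SE by sqrt(1 + n/12):

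- SC only: sqrt(1 + 36/12) = 2.00
- With IV: sqrt(1 + 42/12) = 2.12

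The omitted SE of the placebo mean is SD/sqrt(12), or 6/3.46 = 1.7 ms for an assumed SD of 6 ms.

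**Simulation at Cmax, no true effect.** There were 36 SC active, 6 IV (12 h onward) and 12 placebo participants, with 2000 trials per setting and REML random-intercept fits. The SC schedule has nine times to Day 15 with both a triplicate ECG and a PK sample (6, 12, 24, 48, 72, 96, 120 and 168 h, and Day 15). PK was one-compartment and scaled to Table GZHA.2: CL/F = 0.15 mg / 7670 ng.h/mL = 19.6 mL/h, and AUC/Cmax = 7670/31.2 = 246 h. The documents give no SDs, half-life or PK variability. Those in the table are assumed, as are 20-30% PK between-subject variability and an IV bioavailability ratio of 1.

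| Between SD, residual SD (ms), half-life (h) | Coverage of nominal 90% CI | Mean SE v true SD (ms) | Slope rejection at 5% | Joint-model coverage |
|---|---|---|---|---|
| 4, 6, 120 | 72.6% | 1.54 v 2.35 | 15.0% | 90.1% |
| 6, 6, 120 | 69.3% | 1.82 v 2.99 | 16.7% | 90.6% |
| 8, 6, 120 | 67.5% | 2.05 v 3.51 | 16.9% | 91.0% |
| 3, 7, 120 | 76.8% | 1.50 v 2.13 | 11.8% | 90.5% |
| 6, 6, 96 | 69.4% | 1.74 v 2.90 | 16.3% | 89.7% |
| 6, 6, 150 | 69.7% | 1.93 v 3.13 | 17.2% | 90.2% |

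The reported SE is 58% (2.05/3.51) to 70% (1.50/2.13) of the true SD. With a t multiplier of about 1.68, each limit is off by (2.13 - 1.50) x 1.68 = 1.1 ms up to (3.51 - 2.05) x 1.68 = 2.5 ms. Leaving out IV in the first four settings gives coverage of 67.5-75.0%. Adding Days 29 and 43 at 6, 6, 120 gives 66.1% coverage and 18.5% slope rejection.

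**Is the placebo mean the cause?** A separate simulation, with a half-life of about 143 h and SDs of 3-8 ms (between) and 4-8 ms (residual), gave 63-76% coverage and 10-18% slope rejection. At 6/6 ms it gave:

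- 12 placebo participants: 69% coverage, true SD 3.06 ms
- 1000 placebo participants: 90% coverage, 5.7% slope rejection, true SD 1.90 ms
- 2 placebo participants, as if means were taken within cohort: 44% coverage, 36% slope rejection

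The shortfall disappears when the placebo error does. The added variance with 12 is 3.06² - 1.90² = 5.75 ms². Of this, 6²/12 = 3.00 is the between-subject part, and the remaining 2.75 is mainly the time-specific part.

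**IV times (Protocol section 2).**

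- ECG: IV triplicates on Day 1 are at 0.5, 8 and 12 h; SC triplicates are at 1, 4, 6 and 12 h. IV PK samples exist at 0.5 h and 8 h, so those two pairs have no placebo match.
- Vital signs: IV readings at 15 min, 30 min and 8 h have PK samples but no SC placebo reading. The 5 min reading has no nominal PK partner and does not enter the regression.
- Size for ECG: 6 x 2 = 12 of 6 x 10 = 60 IV pairs, and 12 of 36 x 9 + 60 = 384 active pairs (3%) to Day 15.
- Leverage: SC 0.5 mg Cmax scales to 31.2 x 0.5/0.15 = 104 ng/mL. The modelled initial IV concentration is 118-185 ng/mL, or 7-12% of 1580 ng/mL at 7.5 mg.

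**The case against.** The strongest reply is that little turns on this model. It does not gate escalation, the plan sets no threshold on it, the study is not powered for tests, and the QTcF category counts do not use the double delta. Supine pulse rate and blood pressure get a sound placebo comparison from the vital-sign MMRM, and QRS is not in the regression at all. The sizes rest on assumed SDs, only QTcF was simulated, and the 2.0-2.1 factor holds at the mean concentration (at Cmax the ratio is 1/0.70 to 1/0.58, or 1.4 to 1.7). The 5% slope level is a yardstick, since the SAP names none. At unmatched IV times the double delta is undefined, so software would probably drop those records anyway.

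Much of this stands as a limit on weight. Pulse rate is a fair stand-in for ECG heart rate, so the loss is greatest for QTcF and PR. The IV gap would not merit a comment alone. If IV stays in the vital-sign MMRM, its difference from placebo at 5, 15 and 30 min and 8 h also cannot be estimated, which is a reporting matter.

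None of it removes the defect. An unpowered study may report wide intervals, but a stated 90% CI should cover about 90%. The direction was the same in every setting tried. Fewer placebo participants, because fewer cohorts run or because means are taken within cohort, would generally make it worse.

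**Conclusion.** The concern holds and should be fixed. The planned double-delta regressions leave out the sampling error of the placebo mean. Under the assumptions above, a nominal 90% CI for QTcF at the 7.5 mg geometric mean Cmax covers roughly 68-77%, and a nominal 5% slope test rejects 12-17% of the time with no drug effect. The p-value is too small on average, not necessarily in each dataset. The direction follows from the model itself. The size depends on assumed SDs and PK shape and on pooling about 12 placebo participants. Heart rate, PR and vital signs share the structure, but no figures were computed for them. What is affected is the interpretation of these safety intervals, not dose escalation. The missing IV rule is a minor gap.

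**What to change.** In SAP 9.5.6 and the concentration part of 9.5.5:

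- Model change from baseline, with placebo records kept at concentration 0. Fixed effects: baseline, nominal time, an active/placebo indicator and concentration. Subject is random.
- Report the drug-minus-placebo difference at geometric mean Cmax as the active coefficient plus slope x Cmax, with its 90% CI. Take the slope p-value from the same model.
- Keep the double delta for the scatter plots only.
- Include IV data at times that match the SC schedule (12 h onward). Add one sentence: IV ECGs at 0.5 h and 8 h, and IV vital signs at 15 min, 30 min and 8 h, are reported as change from baseline without placebo correction.
- Leave the vital-sign MMRM model as it is.

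A simulation of this joint model with the baseline covariate gave 90-91% coverage and 5-6% slope rejection. The cost is SAP wording and a few lines of SAS on data already collected. Intervals become wider: at 6/6 ms and a 120 h half-life the SE at Cmax is 2.70 instead of 1.82 ms. In the separate simulation at 6/6 ms the 90% half-width rises from 3.12 to 4.54 ms (4.54/3.12 = 1.46, about 45% wider).
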